The "Robust, Sustainable, Rapid Pragmatic Trials Framework," that includes the RE-AIM model as a central component, is a conceptual framework that can guide the synergistic work of the TSOS study team and NIH Health Care Systems Research Collaboratory in the implementation of the UH3 trial (Figure 3).^{185,190} This framework outlines a series of pragmatic trial approaches including the reach, effectiveness, adoption, implementation and maintenance model as a systematic method for understanding the processes of pragmatic trial implementation. To enhance trial impact, the Robust, Sustainable, Pragmatic Trials Framework encourages trial policy relevance and the collection of policy relevant cost-effectiveness data. The use of mixed quantitative and qualitative methods that comprehensively assess the potential for pragmatic trial/health care system sustainability are also encouraged. Deriving from this framework, the TSOS study pragmatic cluster randomized trial may be best characterized as an hybrid effectiveness-implementation RCT.^{29,50,51,191} The TSOS trial simultaneously aims to determine the effectiveness of the stepped collaborative care intervention model while also assessing the potential utility of the implementation strategy for trauma care systems nationally.^{185,190}

Figure 3. Integration of Large-Scale Pragmatic Trials, Robust Implementation, & Policy Relevance Conceptual Frameworks for Trauma Care Systems

F. A series of innovative methodological approaches are suggested by the combined application of the PRECIS and RE-AIM frameworks in a single pragmatic trial demonstration project targeting PTSD and related comorbid conditions (Figure 3). RE-AIM provides additional pragmatic domains that corroborate and

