$b_{k,0} + b_{k,1}$ *condition _{kt} + e_{ijkt}	Trauma center random effects and error

Y_{ijkt} denotes patient outcome at follow up time i (i=1,2,3,4) (baseline, 3m, 6m, 12m)

for patient j ($j=1,2,...,n_k$)

at trauma center k (k=1,2,...,24)

enrolled in time period t (t=0,1,2,3,4)

For secondary analysis using the repeated measurements from each subject there are two key hypotheses to test. First, the 12-month intervention effect would now be captured by the intervention-by-time interaction specific to the 12-month assessment time: H_0 : β_{11} =0; and evaluation of the intervention effect under this model evaluates any impact of using the partially complete longitudinal data for all subjects to estimate the 12-month intervention effect. This analysis provides a sensitivity analysis evaluating the impact of missing 12-month data for subjects who do have partial follow-up data (e.g. 3 month, 6 month data). A second exploratory hypothesis would be the global null of no intervention effect at all follow-up times, and this would be captured by the multivariate null hypothesis: H_0 : $\beta_8 = \beta_9 = \beta_{10} = \beta_{11} = 0$; and evaluated using a multivariate Wald test. Under this hypothesis the intervention and control means within a given period would be equivalent for all patient follow-up times.

The primary analysis is a single hypothesis test based on Model (A) and will use alpha=0.05. All other statistical tests are conducted to evaluate the sensitivity of the primary analysis to either heterogeneity or missing data, and therefore multiple comparison corrections are not used for these secondary analyses.

Subject Attrition: Some attrition is expected in the study sample due to the research context and the population under study (i.e., low income, ethnoculturally diverse, injured trauma survivors). Prior studies by the

investigative group have consistently achieved follow-up completion rates \geq 75-80% at 12 months post-injury with this population. Estimates derived from these rates are incorporated into the descriptions of subject flow and power analyses.

4. Sample size and power

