
D. Mixed Method Analysis

Mixed methods will be used to integrate the findings from the key informant interviews with pragmatic trial results. The design taxonomy follows a sequential (QUAN \rightarrow qual) structure in which qualitative data collected from key informants will be used to explain quantitative data results from the pragmatic trial.²²⁵ Qualitative data will therefore be used to expand upon the results of the pragmatic trial in order to understand the implementation and policy processes as experienced by key stakeholders. The investigative team will use a mixed method data analytic approach in two ways. First, findings from the quantitative data will be used to identify patterns in the qualitative data. Data derived from the pragmatic trial, such as intervention and control site recruitment periods, will be entered into Altas.ti as a "document family" or attribute of each site provider key informant interview. Analyses would subsequently categorize and compare themes across attribute defined subgroups such as intervention and control group status. Second, the sequential QUAN \rightarrow qual mixed methods design will be used to provide an understanding of pragmatic trial results that require further explanation (e.g., control patients that demonstrate substantial improvement in outcomes, despite not receiving intervention). Results of the mixed method analyses will be presented through a number of modalities that may include key informant narratives, tabular representation of themes with illustrative quotes, and thematic counts.^{225,314,315,322}

E. Exploratory Health Economic Evaluation

1. Background: Health care utilization analyses in trauma care systems

The cost assessments are intended to contribute to an understanding of the resource implications of the UH3 intervention and to American College of Surgeons' and other national policy dialogues of post-injury health service utilization and costs.⁹⁶⁻¹⁰⁵ We note that in our prior policy collaboration with the American College of Surgeons', health care resource utilization and cost findings have contributed to, but have not dominated the discussions related to the establishment of mandates and best practice recommendations for PTSD and comorbidity.⁶³ The health care resource utilization and cost analyses therefore constitute an important exploratory aim of the investigation.

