All units of service will be assigned standard procedure codes (e.g., *Current Procedural Terminology, Fourth Revision* codes) for procedures, Diagnostic Related Groups (DRGs) for hospitalizations, and National Drug Codes for prescribed medication.³²³ These codes will be converted into costs by using the Medicare reimbursement fee schedule for 2014. We will employ a validated and standardized program, EZ Fees 2014 http://www.rbrvs.net/, in this procedure.³²⁴ The EZ Fees program has the 2014 Medicare fee schedule and is frequently updated as payment changes. For services not covered by Medicare, we will use the prevailing fees available from aggregate hospital data at http://hrsa.dshs.wa.gov/rbrvs./. These codes will be translated into unit prices using the Resource Based Relative Value Scales underlying Medicare payment rates for visits of different types, using EZ Fees http://www.rbrvs.net/. Medication costs will be ascertained using the Federal Supply Schedule for a given medication based on its NDC code.³²⁵ All costs will be converted to 2018 using the PHC and PCE indices http://meps.ahrq.gov/about_meps/Price_Index.shtml.

Effectiveness/utility assessments. Exploratory analyses of cost-effectiveness will be conducted only if we find robust treatment effects for PTSD and comorbidity. Gold et al. have suggested the use of generic preference-based utility measures for cost-effectiveness analyses for comparability.²¹⁷ However, because of the unique characteristics of psychiatric populations, mental health services researchers frequently employ disease specific effectiveness measures.^{221,224,326} The study team may explore a series of policy relevant effectiveness measures. The study team may use a method employed in a number of mental health effectiveness trials^{221,224,326} to derive a disease specific clinical outcome entitled "PTSD-free days." The investigative team will also use the Time Trade-Off procedure to estimate health-related quality of life weights longitudinally, which could be used to calculate Quality of Life Adjusted Years (QALYs). Finally, the investigation may also employ the MOS SF-12, to ascertain a generic preference-based utility estimate that has been previously used with injured patients in prior study team investigation.^{243,262,327-329}

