Cost analyses. The investigation's exploratory cost analysis will first compare total costs for patients in the intervention and control conditions; total costs will be the primary dependent variable for this analysis. Total costs include the costs of the intervention, medication and health service utilization (i.e., inpatient, skilled nursing facility, emergency room, and outpatient utilization). After the total cost comparison is completed, other exploratory analyses will compare intervention and control costs restricted to intervention costs and costs of emergency department and hospital admissions. Randomization should ensure balance between the two groups in pre-injury utilization. So, our primary analyses will be to study incremental costs, effectiveness and cost-effectiveness without any adjustments. As a sensitivity analysis the study team will examine patient self-report data to assess balance between the two and to determine if adjustments are necessary. If adjustments become necessary, we will use non-parametric methods previously employed by Drs. [name] and [name].^{135,224} The choice of non-parametric methods, such as propensity score weighting, is mainly because of the sample size of our analyses, where complicated regression models will be difficult to fit. Standard errors and 95% confidence intervals for incremental costs, effectiveness and cost-effectiveness will be obtained using

clustered bootstrapping.224,330,331

A. Study Governance

The study organizational structure and governance plan aims to simultaneously optimize diverse stakeholder input into the trial design and implementation while maintaining the proposed study timeline and UH3 milestone completion. The study organizational structure is outlined in Figure 17.

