With regard to aim 1, the conduct of the pragmatic trial demonstration project, in the beginning of the UH3 year 2, the study team will continue to work toward site readiness for protocol implementation across the 24 sites. This preparation includes finalizing IRB approvals, ensuring site information technology readiness for protocol implementation, and completing all other requisite pre-randomization procedures (Appendices 1, 3, 8, 9). Other year 2 milestones include protocol registration with clinicaltrials.gov, the initiation of tri-annual NIMH DSMB report submission, and submission of the clinical trial protocol manuscript for publication (Table 13). Milestones related to protocol control and intervention patient recruitment, and intervention training workshop completion will occur over the course of years 2-4 of the study as dictated by the stepped wedge intervention rollout (Figure 2, Figure 16, and Table 13). Data analyses and primary outcome manuscript submission will occur in UH3 year 5.

With regard to aim 2, evaluation of the trial implementation process, and ongoing RE-AIM and health economic data collection will occur over the course of the UH3 study. RE-AIM and health economic data analyses will coincide with primary trial data analyses in year 5 of the study (Table 13). For Aim 3, protocol dissemination and annual American College of Surgeons' stakeholder policy discussions will occur over the course of UH3 years 2-4. As with previous American College of Surgeons' policy summits orchestrated by the study team, in the later part of UH3 year 4 more regular (e.g., monthly) policy summit planning meeting phone conferences will occur. These planning calls will be designed to incorporate input from NIH program staff, Collaboratory Steering Committee members, and other key stakeholders. This intensive planning in UH3 years 4-5 will culminate in the UH3 year 5 American College of Surgeons' Committee on Trauma Policy Summit.

Contingency of UH3 milestone attainment on timely NIMH DSMB, IRB and information technology progression. The milestones progression presented in Table 13 below are contingent upon timely progression of coordinated NIMH DSMB and IRB review of the protocol. Delays in these or other regulatory approvals could push back the scheduled milestone completions presented in Table 13. Similarly, delays in site information technology assessments and/or implementation could serve to set back the scheduled milestone completion timeline.

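### The exploratory cost-effectiveness analysis depends on an undefined robust treatment effect, while the cost analysis text plans it without a condition

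*Combined protocol and SAP*

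**What the plan says.** The relevant text is in section E, Exploratory Health Economic Evaluation.

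- **Effectiveness/utility assessments:** "Exploratory analyses of cost-effectiveness will be conducted only if we find robust treatment effects for PTSD and comorbidity". No definition of *robust* is given. The candidate effect measures are PTSD-free days, quality-adjusted life years from the Time Trade-Off, and an SF-12 utility.
- **Cost analyses:** "exploratory cost analysis will first compare total costs for patients in the intervention and control conditions". After a remark on balance between the groups, the text continues: "So, our primary analyses will be to study incremental costs, effectiveness and cost-effectiveness without any adjustments". It then says: "Standard errors and 95% confidence intervals for incremental costs, effectiveness and cost-effectiveness will be obtained using" a clustered bootstrap. No condition on the effectiveness result appears here.
- **Background to the same section:** "The health care resource utilization and cost analyses therefore constitute an important exploratory aim of the investigation".

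Elsewhere, the plans and milestones section schedules the work without a condition: "RE-AIM and health economic data analyses will coincide with primary trial data analyses in year 5 of the study". The conceptual framework section cites a framework that "encourages trial policy relevance and the collection of policy relevant cost-effectiveness data".

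**The concern.** Cost-effectiveness combines a cost difference with an effect difference, and the effect difference is the denominator of the ratio. If the ratio is computed only after that effect has been judged favourable, the reported ratio is selected on its own denominator. The effect entering it is then, on average, too large.

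The condition also removes the joint analysis where it would be most informative, when the effect is modest or uncertain and value depends on how costs and effects move together. The plan itself notes, under its approach to cost analyses, that admissions for new injury may respond to care management.

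Because *robust* is undefined, the decision would be taken after the results are known and without a rule. The statistical analysis plan lists four outcomes, each in continuous and dichotomous form, at three follow-up times. Requiring effects on both PTSD and comorbidity could mean one of these or several. The intended audience is a policy summit.

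**Working it through.** **1. The two passages side by side.** After a null effectiveness result, the effectiveness/utility text says that cost-effectiveness is not analysed. The cost analyses text includes it among the unadjusted analyses, with intervals, and the milestones place health economic analysis in year 5. Neither of these repeats the condition.

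**2. What stays in place after a null result.** Three items carry no condition: the total-cost comparison, the comparisons restricted to intervention costs and to emergency department and hospital admission costs, and the detailed impact inventory of the intervention. Only the cost-effectiveness analysis is lost.

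**3. The plan's precision, reproduced first.** Inputs from the stepped wedge and sample size sections and Tables 10 and 11: 24 sites, four waves of 6, periods t = 0 to 4, 40 patients per site, 25% attrition (30 per site, so 6 per site and period), autocorrelation 0.7, alpha 0.05, power 80%. The primary test is stated thus: "The primary analysis is a single hypothesis test based on Model (A) and will use alpha=0.05". Sidedness is not stated; I take it as two-sided.

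The model is a Hussey-Hughes stepped-wedge variance with fixed period effects and a random site intercept. The standard error is multiplied by √(1 − 0.7²) = 0.714 for the baseline covariate. The minimum detectable effect is (1.96 + 0.84) × SE = 2.80 × SE.

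| ICC | SE before baseline adjustment | SE after | Detectable effect | Table 10 |
|---|---|---|---|---|
| 0.005 | 0.1080 | 0.0771 | 0.2161 | 0.216 |
| 0.010 | 0.1101 | 0.0786 | 0.2203 | 0.220 |
| 0.020 | 0.1133 | 0.0809 | 0.2267 | 0.227 |
| 0.030 | 0.1155 | 0.0825 | 0.2311 | 0.231 |

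Table 10 reproduces. At the PTSD Checklist ICC of 0.02 in Table 11, SE = 0.0809.

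**4. Illustration of the selection.** Assumption: *robust* means p<0.05 in favour of intervention on the 12-month PTSD Checklist alone. The estimate must exceed c = 1.96 × 0.0809 = 0.1586. For a true effect d, let k = (c − d)/SE. Then

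- P(analysis run) = 1 − Φ(k)
- mean estimate, given that it is run = d + SE × φ(k)/[1 − Φ(k)]

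Worked case, d = 0.15: k = 0.0086/0.0809 = 0.106; P = 0.458; mean = 0.15 + 0.0809 × 0.3967/0.4577 = 0.220; 0.220/0.15 = 1.47.

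| True effect (SD) | Analysis skipped | Mean estimate if run | Inflation |
|---|---|---|---|
| 0.15 | 54% | 0.220 | 1.47 |
| 0.20 | 30% | 0.241 | 1.20 |
| 0.227 | 20% | 0.255 | 1.12 |
| 0.34 | 1% | 0.343 | 1.01 |

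The value 0.34 is the team's previously observed effect and 0.227 is the Table 10 figure. The values 0.15 and 0.20 are my choices, to show smaller effects.

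**5. Effect on the ratio.** Suppose the incremental cost is fixed and positive and the Checklist is the effect measure. Integrating 1/x over the selected estimates, the mean ratio differs from the ratio at the true effect by −29%, −13%, −6% and +5% at the four values.

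**6. Other effect measures.** Assume a measure with the same standardised effect and precision as the Checklist, whose estimate correlates ρ with the Checklist estimate. Its inflation is 1 + ρ × (Checklist inflation − 1). For ρ of 0.3 to 0.7 (assumed; not in the documents), 1.47 becomes 1.14 to 1.33, and 1.12 becomes 1.04 to 1.09.

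**The case against.** The strongest case against the point is that the condition is stated in advance, applies to an evaluation labelled exploratory, and leaves the primary PTSD test untouched. The plan also says that cost findings have not dominated earlier policy discussions. All of this stands, and it limits the weight of the point without removing it: an undefined condition stated in advance still leaves the decision open.

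A reader might infer several stronger things that the documents do not support.

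- *That a null result leaves no economic analysis.* The cost comparisons and the impact inventory are unconditional, so savings from fewer admissions could still be seen.
- *That the plan flatly contradicts itself.* The word *primary* in the cost analyses text follows a remark on balance and precedes a sensitivity analysis with adjustment. It most naturally means unadjusted as opposed to adjusted, within an exploratory evaluation. One passage can be read as saying whether the analysis is run and the other as saying how. The wording still needs aligning.
- *That cost-effectiveness would be reported only when it looks favourable.* The condition is on effect, not on cost or on the ratio; a reported ratio could still be unattractive.
- *That cost per unit of effect is understated by one minus the reciprocal of the inflation (32%, 17%, 11% and 1%).* The mean of a ratio does not behave that way; step 5 of the working gives the figures. If incremental cost is negative, an understated cost per unit has no useful meaning.

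It is also fair to object that the SE of 0.081 belongs to the baseline-adjusted primary model, whereas the economic analyses are unadjusted, and that the Checklist score is not among the effect measures named for the economic evaluation. The figures therefore illustrate the mechanism; they do not estimate bias in the planned analysis.

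**Conclusion.** The concern holds in a limited form. The plan makes cost-effectiveness conditional on an effect whose required strength is undefined, and the adjoining text plans the same analysis without that condition. Followed as written, the condition selects the ratio on its own effect estimate and gives no joint cost and effect estimate when the effect is small or uncertain.

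The size depends on the unknown true effect. Under the assumed p<0.05 rule on the Checklist, selection is negligible at the previously observed 0.34 SD. At the plan's detectable effect of 0.227 it means 12% inflation and a one-in-five chance of no cost-effectiveness analysis. At 0.15 it means 47% inflation and a chance of no analysis slightly above one half. A rule that also required comorbidity effects would skip the analysis more often. QALYs or PTSD-free days would be inflated less, to a degree set by their correlation with the Checklist. The trial's primary conclusion is not affected.

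**What to change.** Delete the condition from the effectiveness/utility text and align that text with the cost analyses text. State that incremental cost, incremental effect and their joint uncertainty will be reported whatever the effectiveness result, as net benefit or an acceptability curve from the clustered bootstrap already planned. Keep the exploratory label, and say explicitly that *primary* in the cost analyses text means the unadjusted analysis.

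The cost is one deleted sentence, a small wording change and a little more analyst time. The utilisation, medication and Time Trade-Off data are collected in any case.

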protocol. The stepped wedge design randomizes level I trauma center sites to sequentially initiate the intervention, thus allowing within site pre-, post- intervention comparisons, as well as between site comparisons. An additional advantage of the stepped wedge design for the UH3 protocol is that it would be impractical to roll out the entire intervention at 24 sites simultaneously. Finally, from an implementation science perspective there is an advantage to having the intervention ongoing at the end of the study at every site, should the intervention demonstrate a significant impact on PTSD and comorbidity. Given that there is little threat of contamination at each site across intervention and control patients and that the UH3 can accommodate the increased potential length of active recruitment and follow-up, the stepped wedge design appears to be an optimal choice for the UH3 protocol. In the proposed UH3 protocol stepped wedge design, all 24 participating level I trauma centers are randomly assigned to 1 of four waves. Each wave is assigned a specific proportion of control and intervention patient recruitment. Wave 1 recruits 8 control and 32 intervention patients, wave 2 recruits 16 control and 24 intervention, wave 3 recruits 24 control and 16 intervention and wave 4 recruits 32 control and 8 intervention patients. Interventions are initiated in the second six months of the UH3. The proposed stepped wedge design is outlined in the figure below.

Figure 16. Stepped Wedge Cluster Randomized Design

The stepped wedge regression model will adapt the functional form given below, and uses a timedependent variable to code treatment status for cluster *k* at calendar time *t*, denoted as condition_{kt.} For the stepped wedge study design there are now two key time scales: Period, which denotes the study period measured relative to the calendar time when the overall study begins; and Follow-up time which is a patientspecific time scale relative to when they enrolled in the study. In this model mean outcomes may have a temporal trend in calendar time and this will be captured by modeling "Period", while the primary outcome will still be the 12-month patient outcome denoted by Y_{ijkt} where i=4.

A) The primary analysis regression model will adapt the functional form given below:

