Health services utilization and medication use following index hospitalization will be collected based on self-reports. For the purposes of the analyses, hospital and emergency department admissions will be categorized as: 1) hospitalization/emergency department visits related to the original index injury admission, 2) hospitalization and emergency department visits related to a new injury, and 3) a non-injury related hospitalization (e.g., hospitalization for a chronic medical condition such as congestive heart failure).

Costs of intervention are likely to be dwarfed by the total costs of post-injury care, which would make it difficult to estimate the incremental costs of intervention precisely, given our sample size. This is mainly because our prior investigations suggest that up to 15-20% of injured trauma survivors in both intervention and control conditions experience recurrent injury emergency department and hospital admissions related to the index injury event, increasing the variance of the cost estimators. We will therefore provide detailed impact inventory for the intervention to identify specific components of total costs. Also of relevance, preliminary studies by the investigative group suggest that emergency department and hospital admissions for a new injury are policy relevant outcomes that are potentially malleable by care management interventions targeting PTSD and related comorbidity.^{11,55,220}

3. Costing procedures

The following categories of costing information will be collected: 1) total charges for the index injury visit will be extracted either from the hospital trauma registry or the hospital EHR as available across the 24 level I trauma center sites, 2) all follow-up hospital, emergency department, and outpatient visits and re-hospitalizations over the course of the 12-months after the injury will also be collected from patient 3-, 6-, and 12-month self-report data or from the trauma registry, 3) structured patient interviews will be used to assess medication use.

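### The exploratory economic evaluation makes a crude intervention-control contrast primary, although the stepped wedge enrols intervention patients later on average, so a net calendar trend would bias it

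*Combined protocol and SAP*

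**What the plan says.** Section E, Exploratory Health Economic Evaluation, gives this rationale in its Cost analyses paragraph: "Randomization should ensure balance between the two groups in pre-injury utilization". It then concludes: "So, our primary analyses will be to study incremental costs, effectiveness and cost-effectiveness without any adjustments". Total cost is compared first. After that, "other exploratory analyses will compare intervention and control costs restricted to intervention costs and costs of emergency department and hospital admissions".

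Adjustment is a fallback. Self-report data are examined for balance as a sensitivity step. If adjustment is judged necessary, non-parametric methods such as propensity weighting are preferred because "complicated regression models will be difficult to fit" at this sample size. Standard errors come from a clustered bootstrap, and Costing procedures converts all costs to 2018 values. Period is not mentioned.

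The Statistical Analysis Plan treats the clinical outcome differently. Its section 3 says: "In this model mean outcomes may have a temporal trend in calendar time and this will be captured by modeling" Period. Model A carries four period indicators, the baseline value and a trauma center random effect.

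**The concern.** The rationale fits a trial that randomizes patients. Here 24 sites are randomized to four waves, and within each site all controls come first (Design Overview; Statistical Analysis Plan, section 3). The conditions overlap across sites in the middle periods, but intervention patients are enrolled later on average. A net calendar trend in utilisation, case mix or outcome therefore enters the crude incremental cost and the crude incremental effect.

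The listed safeguards do not remove this from the primary contrast:

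- The balance check relies on self-report data and leads to weighting only if adjustment is judged necessary. In the equal-period layout below, weighting on period would have no overlap in the first period (all control) or the last (all intervention).
- The clustered bootstrap deals with variance, and the 2018 conversion deals with prices.
- The impact inventory ("We will therefore provide detailed impact inventory for the intervention to identify specific components of total costs") itemises components. Delivery cost taken from logs and notes is not exposed to the trend, but the emergency department and hospital cost contrast remains crude.
- One gate exists, "Exploratory analyses of cost-effectiveness will be conducted only if we find robust treatment effects for PTSD and comorbidity", but it does not cover the total-cost contrast or the emergency department and hospital contrast.

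Approach to cost analyses expects intervention cost to be small beside total post-injury cost, so a modest utilisation trend could be comparable to the increment sought.

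**Working it through.** **Inputs.** 24 sites with 40 patients each; control/intervention splits per site of 8/32, 16/24, 24/16 and 32/8 (Design Overview); five enrolment periods, 0 to 4 (notation under Model C); 25% attrition, ICC 0.02 and autocorrelation 0.7 for the PTSD Checklist (Table 11). Assumed, because Figure 16 is not shown: six sites per wave and eight patients (six completers) per site-period. No SD, ICC or trend is given for costs, so results are in SD units using the PTSD Checklist planning values.

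**Reproducing the plan's figure.** Set total variance to 1. Then τ² = 0.02 and σ² = 0.98/6 = 0.1633 for a site-period mean. For 24 sites and 5 periods with fixed period effects and a random site intercept, U = 60, W = 1080 and V = 180:

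- Var = 24σ²(σ² + 5τ²) / [(24U − W)σ² + (U² + 120U − 5W − 24V)τ²]
- = 1.0323 / (58.8 + 21.6) = 0.01284, so SE = 0.1133.
- Minimum detectable effect = (1.960 + 0.842) × 0.1133 × √(1 − 0.7²) = 0.227.

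Repeating this at ICC 0.005, 0.01 and 0.03 gives 0.216, 0.220 and 0.231. All four values match Table 10.

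**Timing by condition**

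| Period | 0 | 1 | 2 | 3 | 4 | Mean |
|---|---|---|---|---|---|---|
| Control | 192 | 144 | 96 | 48 | 0 | 1.0 |
| Intervention | 0 | 48 | 96 | 144 | 192 | 3.0 |

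The Table 13 milestones imply yearly shares in years 2, 3 and 4 of 30/40/30% for controls (mean year 3.00) and 5/35/60% for intervention (mean 3.55), a gap of 0.55 year.

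**Crude SE.** Each of the 120 site-period cells has weight ±1/60. Var = 0.02 × 120/3600 + 0.1633 × 120/3600 = 0.00611, so SE = 0.0782.

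**Bias and exclusion of zero under the null.** Bias b = trend × gap. P(95% interval excludes 0) = 1 − Φ(1.96 − b/0.0782) + Φ(−1.96 − b/0.0782).

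| Timeline | Assumed trend | Bias (SD) | Excludes 0 |
|---|---|---|---|
| Layout, per period | 0 | 0 | 5% |
| | 0.02 | 0.04 | 8% |
| | 0.05 | 0.10 | 25% |
| | 0.10 | 0.20 | 73% |
| Table 13, per year | 0.05 | 0.0275 | 6% |
| | 0.10 | 0.055 | 11% |
| | 0.20 | 0.11 | 29% |

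The 73% row is extreme. It needs a drift of 4 × 0.10 = 0.40 SD over the trial, larger than the 0.34 prior effect cited in Sample size and power.

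A one-off shift S at the start of period 1, 2, 3 or 4 gives bias of 0.4S, 0.6S, 0.6S or 0.4S. On Table 13 it gives 0.25S after year 2 (95% − 70%) or 0.30S after year 3 (60% − 30%). A quadratic trend about period 2 averages 2.0 in both conditions and cancels.

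**With period and site terms.** In 4,000 simulated null trials with a trend of 0.05 SD per period, the crude estimate averaged 0.098 SD and the adjusted estimate −0.001 SD. The adjusted SE is 0.113 without a covariate. Multiplying by √(1 − r²) gives 0.108, 0.098 and 0.081 for a baseline covariate with r = 0.3, 0.5 and 0.7.

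**Break-even on mean squared error,** √(SE_adj² − SE_crude²), comparing the fix with the plan's crude contrast:

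- no covariate: √(0.01284 − 0.00611) = 0.082 SD, which is 0.041 per period (÷ 2) or about 0.15 per year on Table 13 (÷ 0.55)
- r = 0.5: 0.059 SD
- r = 0.7: 0.021 SD

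**The case against.** The SD scale may flatter the problem. No coefficient of variation (CV) is given for cost. Real utilisation growth of 1%, 2% and 5% per period gives spurious cost differences of 2.0%, 4.0% and 10.2%. At an assumed CV of 1 the interval excludes zero in about 5.8%, 8.1% and 26% of null trials, but at CV 2 in only 5.2%, 5.8% and 10%. This stands: the higher error rates need large cost drifts if costs are very variable.

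Table 13 is the only documented timeline, and matching Table 10 supports the power model rather than the enrolment dates. If a period is six months, the layout gap is 1.0 year against 0.55, and a drift of 0.10 SD per year gives 25% on the layout but 11% on Table 13. This also stands, though both sources agree on direction.

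Part of the fall in the break-even comes from the covariate. If the crude estimator had it too, period and site terms alone would break even at 0.071 SD (r = 0.5) and 0.059 SD (r = 0.7). That answers a different question, because the plan's contrast has no covariate.

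Cohort drift checks, screen-in comparisons and registry comparisons are planned, and a case-mix shift visible in pre-injury utilisation could be detected and weighted. These help with case mix. They do not address drift in usual care or outcome, and the primary contrast stays crude.

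Model A was planned for a symptom score, not for costs driven by readmissions, and no figure is given for the net increment, which includes utilisation offsets. Both points are fair. The first is a reason to keep the site bootstrap; the second means the comparison of trend with increment is qualitative only.

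**Conclusion.** The concern holds, with minor weight. The reason given for leaving the primary economic contrasts unadjusted does not apply to enrolment date, and the plan already models calendar time for its clinical outcome. The direction of the timing imbalance follows from the control-first order and from Table 13. Its size in periods assumes equal waves and equal recruitment per period, and the trend itself is wholly an assumption.

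The stakes are limited. The aim is exploratory, the plan itself warns that incremental cost will be hard to estimate precisely, and it notes that in past College work "health care resource utilization and cost findings have contributed to, but have not dominated the discussions". Model A's test of the PTSD outcome is unaffected.

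**What to change.** In Cost analyses, replace the unadjusted primary specification with wording such as:

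> Incremental cost and incremental effect will be estimated with period indicators and a site effect, as in Model A, adding baseline utilisation or baseline SF-12 utility where collected. Confidence intervals will use the bootstrap clustered by site. Crude contrasts will be reported as descriptive, alongside the impact inventory. The same applies to the contrast restricted to emergency department and hospital costs.

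Table 9 lists both the health services and cost items and the SF-12/36 at the ward assessment, so no new data are needed. The work is SAP wording and modest analysis, in a form already planned on the same 24 sites.

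The price is precision: without a covariate the SE is about 1.45 times larger (0.113/0.078). For trends below the break-even, the gain is an interval centred on the right value rather than a smaller error. The correlation of baseline with follow-up cost is not given, so how much precision a covariate would recover is unknown.
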